## 1 DEFINITIONS AND ABBREVIATIONS

Term	Description
ADE	Adverse Device Effect
AE	Adverse Event
CI	Cochlear Implant
CIP	Clinical Investigation Plan
CIR	Clinical Investigation Report
CRF	Case Report Form
CRO	Contract Research Organisation
CSEP	Custom Sound EP
CVC	Consonant-Vowel-Consonant
CSS	Custom Sound Suite
DD	Device Deficiency
DTT	Digit Triplet Test
EC	Ethics Committee Synonymous abbreviations/terms include: IRB (Institutional Review Board) IEC (Institutional Ethics Committee or Independent Ethics Committee) HREC (Human Research Ethics Committee)
eCRF	Electronic Case Report Form
EDC	Electronic Data Capture
EFP	Extensible Fitting platform
EMA	Ecological momentary assessment
EOS	End of Study
FAMHP	Federal Agency for Medicines and Health Products (Competent Authority Belgium)
FF	Free Field
GCP	Good Clinical Practices
Home environment	The subjects personal every-day environment. This can be any situation or location outside of the clinic or research facility.
IB	Investigator's Brochure
ICF	Informed Consent Form
ICMJE	International Committee of Medical Journal Editors

Term	Description
IDMC	Independent Data Monitoring Committee
IFU	Instructions for Use
MDPQ	Mobile Device Proficiency Questionnaire
MPA	Medical Product Agency (Competent Authority Sweden)
MRA	Mobile Research App
MRA-C	MRA cloud component backend infrastructure
MRA-M	MRA iOS-compatible mobile application
MRA-W	MRA web application
NH	Normal Hearing
NR	No Response
PI	Principal Investigator
PIL	Principal Investigator List
QNR	Questionnaire
SADE	Serious Adverse Device Effect
SAE	Serious Adverse Event
SD	Standard deviation
Sensitive personal information	Personal information relating to racial or ethnic origin, political opinions, religious or philosophical beliefs, trade union partnership, genetic or biometric data, the physical or mental health or sex life or sexual orientation of an individual, or the commission or alleged commission of any offence and any related proceedings and outcome thereof.
SNR50	Signal-to-noise ration required for 50% word understanding
SOP	Standard Operating Procedure
SPIN	Speech in Noise
SRT	Speech Reception Threshold
SSQ12	Speech Spatial and Qualities of Hearing Scale
TIM	Trans Impedance Matrix
TRL	Technology Readiness Level
USADE	Unanticipated Serious Adverse Device Effect
VT	Vibrotactile

## 2 CLINICAL INVESTIGATION SYNOPSIS

Investigation title	Feasibility, prospective, multicentric, cross-sectional investigation to characterize daily impedance fluctuations and satisfaction in challenging listening environments in experienced adult CI recipients using the Mobile Research App (MRA).
Short title	DICE
Investigation number	AI5846
Name of research tool	[REDACTED]
Intended use of research tool	[REDACTED]
Name and description of comparator device/product(s)	Not applicable
Estimated recruitment period	8 months
Expected duration per subject	2 months
Number of subjects planned	50
Number of investigational sites planned	3
Inclusion criteria	
 
• Aged 18 years or older (no upper age limit).
 
• Implanted with CIC4-based implant with a Contour Advance, Slim Straight or Slim Modiolar electrode array with at least 6 months experience.
 
• Candidate is a fluent speaker in the language used to assess speech perception performance, as determined by the investigator.
 
• Willing and able to provide written informed consent.
 

Exclusion criteria	
 
• Score below 3 on the screening subset of questions from the Mobile Device Proficiency Questionnaire (digital literacy check).
 
• A failed ECE1 or ECE2 (i.e. flagged, open circuit or short circuit)
 
• Additional health factors, known to the investigator, that would prevent or restrict participation in the evaluations, including significant visual impairment and/or dexterity issues.
 
• Unable or unwilling to comply with the requirements of the clinical investigation as determined by the Investigator.
 
• Investigator site personnel directly affiliated with this study and/or their immediate families; immediate family is defined as a spouse, parent, child, or sibling.
 
• Cochlear employees or employees of Contract Research Organisations or contractors engaged by Cochlear for the purposes of this investigation.
 
• Current participation, or participation in another interventional clinical study/trial in the past 30 days, involving an investigational drug or device
 

(unless the other investigation was/is a Cochlear sponsored investigation and determined by the investigator or Sponsor to not impact this investigation)

- Pregnant or breastfeeding

### 3 SCHEDULE OF EVENTS

Visit Type	Screening 	Visit 1	Take-home	Unscheduled visit if needed	EOS
Timing of Investigation	NA	Day 0	NA	NA	Week 8
Visit window (±)	NA	NA	NA	NA	± 14 days
Procedures					
Written informed consent	X				
Mobile Device Proficiency Questionnaire	X				
Demographics	X				
Eligibility	X				
Hearing history	X				
Device history	X				
Medical history	X				
Device activation		X		X	
T-levels		X		X	X
Performance measurements					
Speech perception testing – Words in Quiet (free-field)				X	X 

Visit Type	Screening 	Visit 1	Take-home	Unscheduled visit if needed	EOS
Timing of investigation	NA	Day 0	NA	NA	Week 8
Visit window (±)	NA	NA	NA	NA	± 14 days
Speech perception testing – Digit Triplet Test in noise (MRA)			X 	X	
Speech perception testing – Sentences in noise (free-field)				X	X 
Unaided Pure-Tone Audiogram (headphones)		X		X	X 
Objective measurements					
Complex impedance/TIM (CSS)		X		X	X
Complex impedance/TIM (MRA)		X	X 	X	X
Data collected with iOSsmartwatch (Temperature, stress level, activity)			X 		
Questionnaires and audio recording					
Wellbeing questionnaire (MRA)			X 		
SSQ12 questionnaire (MRA)		X		X	
EMA (incl. audio recording) (MRA)			X 		
Other					
Concomitant medications/therapies	X	X			X

Visit Type	Screening 	Visit 1	Take-home	Unscheduled visit if needed	EOS
Timing of Investigation	NA	Day 0	NA	NA	Week 8
Visit window (±)	NA	NA	NA	NA	± 14 days
Adverse Events	X	X	X		X
Device Deficiencies		X	X		X
Device exposure		X	X		X
Map settings/Programs from sound processor		X			X
Datalogs from sound processor			X 		

Abbreviations: FF: Free field; MRA: Mobile Research App; CSS, Custom Sound Suite; TIM: Trans-impedance Matrix test; SSQ12: Speech Spatial and Qualities of Hearing Scale; EOS: End of Study

The above table is a guide. The test period between the first and last visit is expected to be 8 weeks (+-14 days) for each subject. Visits planned outside of this time window are not reported as deviations. All visit measurements may be obtained remotely, like in the home situation, if preferred by the investigator or subject.

The screening can be combined with visit 1.

These measurements can also be completed at visit 1 if preferred by investigator or subject.

This measurement on visit 2 is conditional. It is only measured in case of residual hearing with the average of pure tone audiogram thresholds on 250 and 500 Hz lower than 70 dB HL.

No protocol deviations will be created for these measurements in case no data/limited data are collected.

## 4 BACKGROUND INFORMATION AND RATIONALE

### 4.1 Introduction

Health of the cochlea can be monitored e.g. through checking the stability of impedances. Currently this information is obtained only during clinical visits in consultation with clinician. However, impedance-based biomarkers have been proposed for fibrous tissue growth along the CI electrode and for inner ear pathology (Shaul et al., 2019), which could possibly predict future residual hearing loss (Choi et al., 2017). Currently we know very little about the normal daily variability of impedances. At-home monitoring would allow for enough data to establish what daily fluctuations are normal or abnormal for a patient and thus flag issues with the health of the inner ear, e.g. to reduce the risk of loss of residual hearing.

## 4.2 Findings of Previous Nonclinical and Clinical Studies

### 4.2.1 Nonclinical Data

Most animal studies investigating impedance fluctuations focus on the period between surgery and a few months postop (Clark et al., 1995; Huang et al., 2007; Needham et al., 2020; Tykocinski et al., 2001; Wilk et al., 2016; Xu et al., 1997). This period is characterized by strong changes due to (1) fibrous tissue formation along the electrode array and (2) passivation and reactivation of the electrode contacts before and after device switch-on, respectively. The latter phenomenon may be the result of Pt-oxidation due to the inactivity of the electrode in this period but might be attributed as well to inflammatory reactions following electrode insertion at implantation. Some studies sample the impedance with an interval of a couple of days. The most intense measurement schedules in literature record the impedance twice a day. Most of the latter studies measure it before and after device switch-on, focusing on the impedance change after overnight inactivity (Needham et al., 2020). Other studies measure the impedance at two unspecified instances (Tykocinski et al., 2001; Xu et al., 1997). As such, these studies do not provide information on impedance changes in a period of a few months post-op.

Only one study was found that investigated impedance changes in four implanted cats during a 4-weeks period six months after implantation. During this period, strong implantation-related modifications of the intracochlear environment are assumed to have settled and normal daily impedance fluctuations may be distinguished more easily. This work by Newbold et al. (2014) recorded the impedance in the morning before device switch-on and several times within four hours after device switch-on. As such, it addresses specifically the effect of overnight inactivity of the cochlear implant and subsequent device switch-on. The study reported a reduction of the impedance with 20% within 15 min after the onset of stimulation. The effect was stronger

for animals exhibiting higher impedances at the implanted electrodes. This study did, however, not provide more insight in impedance changes within a day.

#### 4.2.2 Clinical Data

Studies of impedance fluctuations on humans typically have in common that the sampling interval of the measurements follows that of the routine clinical visits of the subjects. This means a measurement interval of at least one week during the postoperative period up to three months. Thereafter, the interval is at least a couple of months or more (Brkic et al., 2020; Busby et al., 2002; Choi et al., 2017; Jia et al., 2011; Leblans et al., 2022; Molisz et al., 2015; Paasche et al., 2006; Sanderson et al., 2019; Shaul et al., 2019; Tykocinski et al., 2005; Zarowski et al., 2020). Several of them investigate the strong variations directly induced by CI-implantation, either due to electrode passivation/reactivation, tissue formation around the electrode, the influence of medication or surgical procedure on those phenomena, or due to adverse issues related to the electrode (Busby et al., 2002; Leblans et al., 2022; Molisz et al., 2015; Paasche et al., 2006; Tykocinski et al., 2005; von Mitzlaff et al., 2021). Two of the exceptions are (Choi et al., 2017; Shaul et al., 2019). They investigated in the postoperative period of 3 months up to 3 years the relation between impedance changes and episodes of hearing loss, vertigo or tinnitus, using an impedance sampling period of at least a few months. Their work illustrates very well the limitations when monitoring these medical events, which are often transient in nature, by means of in-clinic impedance measurements. They try to correlate substantial impedance increases, which had disappeared in 50% of the cases at the subsequent visit, to medical events that occurred in the period four weeks before and after the observed increase. This raises two questions: (1) How many relevant impedance changes/medical events have been missed? (2) What is the reliability of relating the impedance increase and the medical event in the case of such a broad time interval?

An exception is the work of (Newbold et al., 2014), investigating the effect of overnight inactivity of the cochlear implant and subsequent device switch-on in experienced human CI-users (1.5 – 5.5y postop), which is similar to their animal study. Three CI-users are followed only for three subsequent days, while electrode impedances were recorded three times a day: before device activation in the morning, half an hour later and just before device switch-off at the end of the day. An average impedance reduction of 5% after device switch-on was reported. This study, however, focussed on overnight activity and not on impedance variation throughout the day. Furthermore, the number of datapoints in this study was limited.

[figure not shown]
[figure not shown]
The following work also measured impedances multiple times per day in humans, but during 1-month post-op. Parreño et al. (2020) recorded impedances twice a day (with a 12h difference) over the first 30 days after implantation, using a self-developed system for at-home monitoring. Because the data are acquired before initial stimulation, the data are dominated by huge impedances mostly attributable to the passivation of the electrode contact, building up during the first 2 weeks. Ausili et al. (2022) used the same setup to record complex impedances daily (once per day) over the first 30 days after implantation. The dynamics of total impedance changes between days were similar to the findings by Parreno et al. In addition, it was found that the main contributor to changes are the capacitive components of the impedance. The dynamics of impedances during a day (before and after stimulation) have not been analyzed. Overall, published studies lack information on impedance variation during a day and as day-to-day variation, especially during a period of at least six months post-implantation.

### 4.3 Study Rationale

The possibility to continuously monitor the health of the implanted cochlea, with associated algorithms to detect events such as inflammations and scar tissue formation (fibrosis) will address a major challenge in our field, namely long-term preservation of residual hearing. A candidate biomarker for cochlear health may be found through the measurement of the different components of the complex electrode contact impedances. A prerequisite to develop detection algorithms for abnormal events, is the collection of normative data. However, as mentioned in section 4.2, data on impedance variation during a day and as day-to-day variation, especially during a period of at least six months post-implantation is not currently available. Past studies

analysed clinical impedance measurements retrospectively or data prospectively in-clinic at scheduled visits of the subjects. Consequently, the availability of data is limited to irregular and rather coarse time intervals of week(s) or months, while the phenomena contributing to the impedance often fluctuate on a faster time scale. Therefore, when measuring the impedance in-clinic, it is impossible to control the appropriate sampling times in case of several potential origins of the impedance fluctuations, such as infections of the upper respiratory pathways (Zarowski et al., 2020), (over-night) inactivity of the cochlear implant prior to the measurement, the intensity of implant use, the use of medication, and clinical events such as vertigo, Ménière-like symptoms, tinnitus, and loss of residual hearing (McNeill and Eykamp, 2016; Parreño et al., 2020; Shaul et al., 2019). This motivates the primary objective of this investigation, which is to collect and describe time series data for complex impedances collected at home.

[figure not shown]
[figure not shown]

## 5 RESEARCH TOOL INFORMATION

### 5.1 Identity and Description of the research tool

The primary interest of this investigation is the impedance measurement collected in the home environment of the participant. To collect this data a research system is used consisting of Mobile Research App (MRA) (participant facing app) V3.0 and above.

[figure not shown]
[figure not shown]

For more information, contact the Office of the Vice President for Research and the Office of the Vice President for Student Affairs.

Tumor size	Percentage
0-10 mm	100%
10-20 mm	80%
20-30 mm	50%
30-40 mm	20%
40-50 mm	10%

[figure not shown]
A black and white image consisting of a series of horizontal lines of varying lengths. In the top left corner, there is a small, solid black square. The lines are mostly white on a black background, with some being thin and others thicker. They are positioned in a staggered, non-linear fashion across the frame.

[REDACTED]

All research tools are manufactured by Cochlear Limited. The iOS device® with the MRA installed will be labelled exclusively for use in a clinical investigation. The study data will result in learnings that will be useful towards the design of a future daily impedance feature in the commercial software. CI recipients/investigators will use the research tools for the duration of the study only. Traceability of the build number will be documented in the tracking forms such as the Software Tracking Form (1302326). The investigators will receive comprehensive, specific training in the use of the research tools and in ongoing support during the execution of the study procedures as needed. This training will be logged on a training log. The CI-recipients will receive specific training in the use of the research tool and will receive ongoing support from the investigator during the execution of the study procedures. The research tools are software-only and will not be in contact with body fluid or tissue. Further details regarding the research tools are provided in the IB and Instructions for Use (IFU).

[REDACTED]

[figure not shown]

A horizontal bar chart consisting of 20 black bars of varying lengths. The bars are arranged in two main groups: a top group of 10 bars and a bottom group of 10 bars. The bars in the top group are generally longer than those in the bottom group. The chart is set against a white background with thin black horizontal grid lines.

## 6 OBJECTIVES

### 6.1 Primary Objective

To collect and describe time series data for complex impedances (access resistance & polarization) collected between clinic visits.

## 7 DESIGN OF THE CLINICAL INVESTIGATION

### 7.1 General

[figure not shown]
[figure not shown]
This is a feasibility, prospective, multi-country, multi-centre, cross-sectional interventional clinical investigation in adults with a CE labelled cochlear implant.

The early feasibility categorisation relates to the use of research tools and the purpose of the investigation being to collect pilot data on impedance measurements in real-world environments, reflecting any situation the subjects encounter during their normal life outside of the clinic.

In total, 50 eligible subjects are planned to be recruited in the clinical investigation. The subjects include adults from the age of 18 years or above who are currently using a commercial available Nucleus CIC4-based implant with a Contour Advance, Slim Straight or Slim Modiolar electrode array with a minimum of 6 months experience. Subjects will be screened according to the inclusion and exclusion criteria as described in section 7.2. No Randomisation nor blinding to avoid bias is applicable in this study since there is no comparator.

Subjects will attend two scheduled study visits over a two-month study period as described in the Clinical Investigation Plan (CIP) Schedule of Events (Section 3). At and in between study visits, subjects will undergo hearing assessments and safety monitoring. The time of each visit is estimated to be less than 2 hours. During the first two weeks of the take-home the subjects will start to perform daily impedance test tasks and complete a questionnaire five times a day and a speech test once per day with the MRA application in order to obtain the first primary endpoint, i.e. characterization of Daily Impedance Fluctuations. For the rest of the two months study two daily impedance tests with questionnaire and one speech test will be measured per day. In case of any of symptoms or impacted hearing (sound quality) reported by the participant in the

questionnaire, one additional week of daily impedance tests with questionnaire for five times a day will be done.

Safety will be assessed by recording and summarising all adverse events (AEs)/advice device effects (ADEs) and device deficiencies (DDs). The investigator will be able to view and monitor results during take-home, however this is not required for the study. Given the feasibility nature of this study, characterisation as primary endpoint and monitoring of results by the investigator, the data can be analysed continuously. The purpose is acquiring knowledge at this stage. No data monitoring committee will be used for this clinical investigation. All subjects will attend an End-of-Study visit at the time they complete the study.

The principal Investigator List will specify where evaluations will be conducted and who will be responsible. The principal investigator may determine to do study visit measurements remotely where possible, like in the home situation.

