### 7.2.7.1 Blinding Procedures

This is a pilot study with the aim to collect data on impedances in the home environment to be potentially used to inform larger data collection initiatives for characterisation and/or diagnostic purposes. The subjects will not see the impedance data collected. Blinding is not applicable in this study.

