### 7.3.2.2 Data collection during take-home with MRA

#### 7.3.2.2.1 Complex impedance

The complex impedance measurement is an objective measurement of the characteristics of the electrode-tissue interface (section 4.1) and requires no feedback or interaction by the user. It can be started by the user with a single button press. The measurement data is stored automatically by the system and uploaded to the web portal for off-line analysis. The measurements are expected to be inaudible or at least only perceived as soft sounds.

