### 7.3.3 Safety Evaluations and Procedures

The risks and anticipated ADEs for the investigational device, as identified in Sections 8.2 and 8.3 of the CIP, will be assessed in the clinical investigation via reporting of all AEs/ADEs from the time of first subject first visit until last subject last visit. The stimulation characteristics of the electrode sweep are standard charge-balanced bi-phasic pulses presented sub-threshold, with an associated medium-risk anticipated device effect possible. The subject is requested to complete a well-being questionnaire each day to provide information relating to the association between impedance fluctuations and clinical symptoms, and to capture adverse events. The investigator is required to capture any adverse event or any new information in the CRF on each study visit.

Safety data adjudication will be conducted by the Sponsor in accordance with the Sponsor's standard operating procedures. Upon review of data available in the CRF, the Sponsor may query data or request deidentified source documents to review the event.

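### The visible text does not mask the investigator to take-home impedance, so the eCRF should record whether impedance was seen before an adverse event or unscheduled visit was raised

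*Combined protocol and SAP*

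**What the plan says.** Section 7.1 allows optional access to take-home data: "The investigator will be able to view and monitor results during take-home, however this is not required for the study". The same paragraph gives investigator monitoring as one ground for ongoing analysis: "monitoring of results by the investigator, the data can be analysed continuously". Section 7.3.2.2.1 says that the complex impedance data are "uploaded to the web portal for off-line analysis".

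Masking is described for subjects only. Section 7.2.7.1 reads: "The subjects will not see the impedance data collected. Blinding is not applicable in this study". Section 7.1 gives the absence of a comparator as the reason why blinding does not apply.

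The investigator enquires about adverse events at visits (11.2), enters all of them in the CRF (11.4) and records medication changes there (7.3.3.1). The Schedule of Events (section 3) has a column headed "Unscheduled visit if needed". No visible text states a criterion for that visit or says who decides on it.

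The plan intends to relate such data to impedance. Section 7.1.1 looks for correlations with medical, hearing, medication and device-use data. Section 7.3.3.1 treats the effect of medication on impedance as a secondary objective. Section 7.3.3 says that the subject's daily wellbeing questionnaire is there "to provide information relating to the association between impedance fluctuations and clinical symptoms, and to capture adverse events".

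**The concern.** In the exploratory analyses impedance is the explanatory series, and events, medication and hearing results are what it is set against. If the person recording part of the second group can see the first, a visible change in impedance may lead to closer questioning, an extra visit or an extra entry. Records would then be found more often where impedance moved, and an association could appear or grow with no true link behind it.

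The absence of a comparator does not answer this. It disposes of bias between treatment groups, but not of unequal detection of events according to a visible predictor. Section 4.3 presents these data as a prerequisite for detection algorithms, so an inflated association could carry into later work.

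**Working it through.** The plan states no figure on this point, so there is none to reproduce. The check sets the sections side by side and then adds a labelled illustration.

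**1. Can the investigator see impedance?** Section 7.1 permits viewing of results without defining the word. Impedance is the main take-home result and goes to a portal. Much of section 5.1, which describes the tool, is redacted. Access to impedance is therefore not excluded by the visible text, but it is not stated either.

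**2. Which records could depend on having seen it?** According to the Schedule of Events:

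| Measure | Scheduled | Other occasion |
|---|---|---|
| SSQ12 | Visit 1 | Unscheduled visit |
| Free-field words and sentences | EOS, or visit 1 if preferred | Unscheduled visit |
| Unaided audiogram | Visit 1; EOS only with residual hearing | Unscheduled visit |
| App digit triplet test | Take-home | Unscheduled visit |
| Wellbeing questionnaire | Take-home | None |

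A second SSQ12 exists only for subjects who had an unscheduled visit. As scheduled, the same holds for a repeat free-field score. Adverse events and medication changes entered by the investigator belong with these exposed records.

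**3. Which records are protected?** The questionnaire is completed by subjects who do not see impedance, five times a day for two weeks and then twice a day (7.1). The app speech test is done once a day. The extra intensive week follows from the participant's own report (7.1). The impedance readings need no user judgement (7.3.2.2.1).

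**4. Would the data show the problem afterwards?** Section 11.2 lists the items documented for each adverse event: dates, action, outcome, severity and relatedness. Whether impedance had been seen first is not among them.

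**5. Illustration of size.** Suppose there is no true association. Let *p* be the true event risk, equal in both groups, and let c1 and c0 be the probabilities that an event is recorded with and without a visible fluctuation. The recorded risks are p × c1 and p × c0, so the spurious risk ratio is c1/c0 and the odds ratio is [p·c1/(1 − p·c1)] / [p·c0/(1 − p·c0)]. The values of p, c1 and c0 are assumptions. With p = 0.20:

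- c1 = 0.6, c0 = 0.5: risks 0.12 and 0.10; odds ratio (0.12/0.88)/(0.10/0.90) = 1.23
- c1 = 0.8, c0 = 0.5: risks 0.16 and 0.10; odds ratio (0.16/0.84)/(0.10/0.90) = 1.71
- c1 = 0.8, c0 = 0.4: risks 0.16 and 0.08; odds ratio (0.16/0.84)/(0.08/0.92) = 2.19
- c1 = c0: odds ratio 1

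Section 7.2.3 expects 10 of the 50 subjects to fluctuate. In those 10, the first two cases mean 10 × 0.12 = 1.2 or 10 × 0.16 = 1.6 recorded events, against 10 × 0.10 = 1.0 with recording at 0.5. The difference is less than one event.

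**The case against.** The strongest reply is that the plan already takes its symptom data from the right source. Section 7.3.3 ties the impedance-symptom association to the subject's own questionnaire, and subjects are masked. Adverse events are asked about at visits that take place whatever impedance does. All must be recorded, and source notes must show the enquiry even when nothing is found (11.2). The sponsor adjudicates safety data (7.3.3). The primary endpoint is descriptive, section 9.1 treats any association as exploratory, and open monitoring is a deliberate choice (7.1, 9.8). The secondary endpoints and their analyses are redacted, so no visible text shows that investigator-entered events or unscheduled-visit tests feed a specific impedance analysis.

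Most of this stands, and it limits the reach of the point. It does not close the route. A duty to record everything does not make the search equally hard in every subject and week, and adjudication reviews what is already in the CRF. Section 7.1.1 still intends to correlate medical and hearing data with impedance.

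A reader might infer that investigators call unscheduled visits in response to impedance. The documents do not say who calls them, and a trigger may lie in redacted text. A reader might also set this point against the question in 4.2.2: "What is the reliability of relating the impedance increase and the medical event in the case of such a broad time interval". That question is about sparse clinic sampling, which frequent home measurement does address; it is not about who looks for events.

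**Conclusion.** The point holds in a limited form. The visible text leaves a route by which a seen impedance change could influence which investigator-recorded events, medication entries and unscheduled-visit tests exist, and provides nothing to detect it afterwards. Only exploratory associations that use those records are exposed. The primary descriptive summary, the questionnaire series, the daily app speech test and the extra week are largely unaffected.

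The size is unknown. The odds ratios of 1.2 to 2.2 are correct arithmetic on assumed rates and should not be read as expected bias. They also compare subjects with one another, whereas section 7.1.1 makes each subject their own control.

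Two stronger readings are not supported: that the impedance-symptom association as a whole is compromised, and that the investigator must be masked. The main symptom series comes from masked subjects. Masking until events are entered would have no clear end over eight weeks of accrual, and it would conflict with the open monitoring in 7.1 and 9.8.

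The conclusion assumes that the redacted text neither restricts the investigator's view nor sets the visit trigger. This is a cheap improvement of low to moderate priority.

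**What to change.** Keep open viewing.

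1. On each adverse-event page and each unscheduled-visit page of the eCRF, add the reason or initiator, and a yes/no item: *impedance result viewed before this was raised*.
2. State in section 9 that the impedance-symptom analysis rests on the subject-reported questionnaire and the scheduled tests.
3. Report any analysis that uses investigator-recorded events or unscheduled-visit tests twice, with and without the records flagged yes.

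Medication changes can be taken from the subject's own questionnaire entry, which 7.3.3.1 already provides for, so no item is proposed for that page.

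The cost is one or two extra eCRF items per page and one sensitivity analysis. The items need to be in place during data collection, because the order of viewing and recording cannot be reliably reconstructed later.
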